Study Protocol with Statistical Analysis Plan and Informed Consent Form

Title	Details
Date	6 May 2024
NCT Number	NCT05163964
Study title	Chronotype, Chrononutrition and Glucose Tolerance Among Prediabetic Individuals: Chrono-DM™
Name and Institution of Principal Investigator	[name] [name] Department of Bioscience Faculty of Applied Sciences (FOAS) Tunku Abdul Rahman University Management and Technology (TARUMT) [contact]
Name and Institution of Co-Researchers	[name] [name] Assistant [name] of Food Science and Nutrition UCSI University, Malaysia [contact] [name] [name] Assistant [name] of Reproductive Medicine Duke-NUS Medical School, Singapore [contact] [name] [name] Deputy Dean Faculty of Applied Sciences Tunku Abdul Rahman University Management and Technology (TARUMT) [contact] [name] A/L [name] Physician Department of Emergency and Trauma Hospital Serdang, Malaysia [contact] [name]. [name] Professor, Deputy Dean of Graduate School, Lecturer Faculty of Health Sciences Universiti Kebangsaan Malaysia [contact]
Sub investigators at the site and Co-Researchers	[name] [name] Family Specialist Community Clinic Batu Berendam, [contact]

	
[name] [name] Medical Officer Community Clinic Batu Berendam [contact]
 
[name] Clinical/ Community Dietitian Community Clinic Kuala Sungai Baru Ministry of Health [contact]

Principal investigators at the site and Name of PhD Student	
[name] Department of Bioscience Faculty of Applied Sciences (FOAS) Tunku Abdul Rahman University Management and Technology (TARUMT) [contact]

Study Population	Prediabetic individuals in Community Clinic Melaka
Study Design	
Study Type: Prospective Longitudinal Study Sampling Method: Convenient sampling method

General Objective	To determine the associations of chronotype and chrononutrition with glucose tolerance among prediabetic individuals in Malaysia.
Specific Objectives	
 1) To investigate the effect of chrononutrition on glycemia measures among prediabetic individuals. 2) To investigate the associations of lifestyle factors with glycemia measures among prediabetic individuals. 3) To investigate the associations of anthropometric measurements with glycemia measures among prediabetic individuals.
Study outcomes	
The main outcomes of this study are
 
 1) The change of baseline glycated hemoglobin (HbA1c) among prediabetes adults at 6 months. 2) The change of baseline fasting plasma glucose (FPG) among prediabetes adults at 6 months. 3) The change of baseline 2-hour post-load plasma glucose among prediabetes adults at 6 months. 4) The change of baseline continuous glucose monitoring (CGM) profile among prediabetes adults at 6 months. 
Secondary outcome of this study are
 
 1) The change of eating misalignment among prediabetes adults at 6 months. 2) The change of chronotype among prediabetes adults at 6 months.
Sample Size	120 prediabetic individuals
Study Duration	1 March 2022 until 31 December 2023
Name and Address of Sponsor	Fundamental Research Grant Scheme (FRGS), Ministry of Higher Education/ UMalaya (FRGS/1/2021/SKK06/TARUC/02/1)

Ethics Approval	Tunku Abdul Rahman University Management and Technology Ethics Committee (TAR UC/EC/2021/02-3) Medical Research and Ethics Committee (RSCH ID-21-00114-IVI)
-----------------	---

Executive Summary:

Early meal timing affects the circadian rhythmicity and influenced the postprandial blood glucose level in response to meal in diabetes patients. In the other words, diabetes patients with earlier meal timing had a stable glycemic control compared with those with late meal timing. This is a new concept to switch the meal timing earlier than later in diabetes self-monitoring management. However, there is insufficient evidence from Southeast Asia to determine the optimal-meal-timing and its association with glycemic measures in prediabetes individuals. Hence, this study carried out to determine the associations of chronotype and chrononutrition with glucose tolerance among prediabetic individuals in Malaysia.

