A repeated A1c should be done 4 weeks after the first positive test for asymptomatic patients.

In symptomatic individual, a single positive test is sufficient.

Location of Research:

Location of Research	Expected number of subjects per site
Community Clinic Batu Berendam	56
Community Clinic Bukit Rambai	55
Community Clinic Sungai Udang	55

Recruitment pamphlets that contain general information of the study will be placed in all the healthcare clinics in Malacca. During the process of recruitment, a trained research assistant, clinical dietitian (one of the co-researchers) or family medicine specialist (one of the co-researchers) will inform potential prediabetic individuals of the study both verbally and will be provided written information (Appendix A). Newly diagnosed prediabetic individuals who are agreeable to participate will be provided written informed consent (Appendix A). Study visits (recruitment and follow-up visits) of this study will be determined based on the healthcare clinic appointment schedules. Those who decline to participate continue to receive their routine treatment as usual, and care provided to each prediabetic individual is not affected nor affected by each individual's decision to either participate or not participate in the study. An overview of the study procedure is illustrated in Figure 3. All the newly diagnosed prediabetic individuals who fulfill the inclusion criteria will be invited to participate in the present study. They will be recruited when they visit the diet clinic for the first time for their initial appointment scheduling. This would be considered the baseline visit. OGTT, HbA1c and FBS results will be traced from medical records.

Data regarding sociodemographic information and anthropometric measurements will be collected in the baseline visit. Enrolled participants will be interviewed by a trained

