research assistant using the following questionnaire including (1) Munich Chronotype Questionnaires (MCTQ) (Appendix D), (2) Pittsburgh Sleep Quality Index Questionnaire (PSQI) (Appendix H), (3) Harvard Light Exposure Questionnaire (HLEQ) (Appendix G), (4) International Physical Activity Questionnaire (IPAQ) (Appendix C) and (5) Chrononutrition Profile Questionnaire (CPQ) (Appendix I). Anthropometry measurements including body fat, height, body fat percentage, visceral fat, waist circumference and hip circumference will be measured. Participants are requested to fill up 3-days dietary record (3DDR) (2 weekdays and one weekend day) and the data will be collected in the next visit. Baseline reading of fasting plasma glucose (FPG, OGTT, liver function, and HbA1c) will be retrieved from medical records in the community clinic. Routine treatment will be provided as usual. To minimize the loss of follow-up, phone conversations will be made to ensure the 3-days dietary data is completed.

At the second visit (three months from the baseline), all participants are required to wear a CGMS sensor at the back of their upper arms to measure the 24 hours glucose fluctuation over 14 consecutive days. 3DDR will be given to participants to record their consecutive 3 days dietary record and will be returned after 14 days. After 14 days, participants will return the CGMS sensor at the community clinic. Or alternative way of CGMS sensor collection by an assistant at the participant's home. All questionnaires will be interviewed by a trained research assistant again. Anthropometry measurements including body fat, height, body fat percentage, visceral fat, waist circumference and hip circumference will be measured repeatedly.

At the third visit (six months from the first visit), for FBG, OGTT and HbA1c test, all the readings will be retrieved by the research assistant from the medical record to document the glycemic outcome. The participants will be interviewed by the trained research assistant during all clinic visits using similar questionnaires. All anthropometry measurements (body fat, height, body fat percentage, visceral fat, waist circumference and hip circumference) will be conducted again. 3DDR will be given to record their 3 days dietary intake again and the record progress will be followed up through phone. The original 3DDR will be collected at the routine appointment.

Sample size Calculation:

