The sample size is estimated using G*Power software version 3.1.9.4 (Erdfelder, Faul and Buchner, 1996). To determination of association between chrononutrition and glycemic control, the β -coefficient of 0.13 adopted from Sakai *et al.*, (2018), the power was set to 0.9 with 2 sided significance level and alpha error given 0.05, a total of 83 prediabetic adults expected in this study. To compensate for the non-responding and non-compliance during follow-up, a dropout rate of 50% will be considered, the total sample size required is 166 subjects in the study for 6 months.

Test Family: T Test

Statistical Test: Linear Multiple Regression Fixed Model, single regression coefficient

Tail(s): 2

Effect Size (β -coefficient): 0.13 (Sakai *et al.*, 2018)

α Error prob: 0.05

Power(1- β err prob): 0.90

[figure not shown]
Total Sample Size: 83 prediabetes individuals

50% dropout rate taken as consideration in study for 6 months follow up, total 166 prediabetes individuals shall be recruit in this study.

Dropout Rate:

$$= \frac{83}{1-0.5} = 166 \text{ prediabetic individuals}$$

Figure 3: Flow diagram of the study design

Participants will be undergoing OGTT, FBS and HbA1c tests after an overnight fast of 8-10 hours. This is a routine universal test for prediabetes/ diabetes diagnosis. Participants will be informed to eat their usual diet for three days prior to the test. The diagnostic value for diabetes on plasma glucose. the diagnostic values for prediabetes and diabetes based on OGTT, and the diagnostic values for prediabetes and diabetes based on HbA1c have been shown in Table 1, Table 2 and Table 3, respectively. Fasting blood sample will be taken for FBS and HbA1c tests. Subsequently, participants will be given 75-gram glucose water to drink within 5 minutes. Blood sample will be taken after 2 hours for glucose determination. Participants should rest throughout test with only plain water is allowed to drink. Figure 4 shows the procedure of OGTT. All the tests will be conducted in the healthcare clinic lab. Results will be traced from medical record.

Table 4: Summary of data collection and timeline

Data	Baseline	3 months	6 months
Sociodemographic			
Age	.	.	.
Date of Birth	.	.	.
Marital Status	.	.	.
Education Level	.	.	.
Occupation	.	.	.
Monthly Household Income	.	.	.
Health History	.	.	.
Smoking Habit	.	.	.
Supplementary Consumption	.	.	.
Anthropometry			
Weight	.	.	.
Height	.	.	.
Waist Circumference	.	.	.
Visceral Fat	.	.	.
Body Fat	.	.	.

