Step counts	.	.	.
Questionnaires			
Munich Chronotype (MCTQ)	.	.	.
Pittsburgh Sleep Quality Index (PSQI)	.	.	.
Harvard Light Exposure (HLEQ)	.	.	.
International Physical Activity IPAQ)	.	.	.
Chrononutrition Profile Questionnaire (CPQ)	.	.	.
3 days dietary record (3DDR)	.	.	.
Glycemic Measurements			
Continuous Glucose Monitoring (CGM)	.	.	.
Fasting Plasma Glucose (FPG)	.	.	.
2-hour Post-load Plasma Glucose (2hPPG)	.	.	.
Glycated Hemoglobin (HbA1c)	.	.	.

[figure not shown]

Figure 4 Procedure of OGTT 24-hour

Continuous glucose monitoring system 24-hour CGMS (Freestyle Libre Pro, Abbott, Germany) is a glucose monitoring device that measures interstitial glucose levels and its indicated for detecting trends and tracking patterns in persons with prediabetes/diabetes. Freestyle Libre Pro is not a usual/ normal Freestyle Libre. The normal version of CGMS can be easily purchased in the market, but CGMS Pro version can only be purchased direct from Abbott Germany. For the usual/normal Freestyle Libre, reading must be read by reader every 8 hourly and participants may easily check their blood glucose, resulting the unnecessary bias, where participants might change their diet and lifestyle habit to control the blood sugar. Whereas, pro version can only be used for clinical trial purpose, cannot be commercialized out of clinical trial use. Readings from the 24-hour CGMS Pro version will not be made available to participants in real time, hence, it will prevent the bias that may arise from unmasked real-time glucose reading. Besides, blood sugar can be kept record for up to 14 days for pro version, easier for researcher to collect the data and save the cost of reader. Figure 5 shows the example of the daily glucose summary from 24-hour CGMS. 24-hour CGMS aids in understanding the person glucose profile and detecting episodes of hyperglycemia and hypoglycemia. Figure 6 shows the example of the daily pattern outcome from 24-hour CGMS.

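### The timing of CGM wear is stated inconsistently, and under several of the stated schedules main outcome 4 (CGM change from baseline to 6 months) cannot be computed

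*Combined protocol and SAP*

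**What the plan says.** **Outcome.** The synopsis (Study outcomes) gives as the fourth main outcome "The change of baseline continuous glucose monitoring (CGM) profile among prediabetes adults at 6 months".

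**Visit-by-visit narrative (section 3).** CGM appears at one visit: "At the second visit (three months from the baseline), all participants are required to wear a CGMS sensor", worn for 14 days. Then: "After 14 days, participants will return the CGMS sensor at the community clinic". For baseline the glycemic data are described thus: "Baseline reading of fasting plasma glucose (FPG, OGTT, liver function, and HbA1c) will be retrieved from medical records in the community clinic". For the last visit: "At the third visit (six months from the first visit), for FBG, OGTT and HbA1c test, all the readings will be retrieved" from the medical record. CGM is not mentioned at either of those visits.

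**Device description (section 3, CGM system).** A CGM reading is taken in the 14 days before the second visit, which this section couples with the repeat OGTT. The Introduction places the repeat OGTT in the 6-month period, and the narrative retrieves it at the third visit. A sensor lasts at most 14 days.

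**Exposure measures (section 3).** The second visit is said to fall 14 days before the third.

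**Proposed Research Schedule (section 4).** Both the activity and the milestone tables have sensors distributed at baseline and at the second visit, and collected at the third.

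**Table 4** ("Table 4: Summary of data collection and timeline"). In the text available, the CGM row is marked at baseline, 3 months and 6 months.

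**Study Outcomes and Statistical Analysis.** CGM enters as glucose variability or as a CGM profile, with no mention of change.

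**The concern.** A change from baseline to 6 months needs two measurements at those times. If staff followed the visit narrative as written, neither was taken and no analysis method can recover the change. A single wear supports a CGM level at one time and nothing more. Whether one of the four main outcomes is estimable therefore depends on which section the clinics worked from.

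The analysis text does not help. It never says that the CGM variable is a change, so a 3-month level could be modelled and reported under the synopsis label without anyone noticing the mismatch.

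The timing of this question also matters. The document is dated 6 May 2024, after the planned completion of the third visit (06/03/2024 in the activity table, 31/03/2024 in the milestones). The wears have presumably been done by now, so what remains is to find out which they were and describe them correctly.

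**Working it through.** The plan has no figure of its own to reproduce here. The check sets each stated schedule against the two values that the outcome needs.

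**Inputs.** Second visit at 3 months and third at 6 months (visit narrative); 14-day wear (visit narrative and device description); second visit 14 days before the third (Exposure measures); distribution at baseline and visit 2, collection at visit 3 (section 4).

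**Assumptions.** One month = 365.25/12 = 30.44 days. Wear starts on the day the sensor is given, unless the text ties it to a later visit. A wear starting at baseline counts as a baseline value. A wear ending or starting at the third visit counts as a 6-month value.

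**Days from baseline.**
- 3 months: 3 × 30.44 = 91.3. A wear from then ends at 91.3 + 14 = 105.3.
- 6 months: 6 × 30.44 = 182.6. The narrative's wear ends 182.6 − 105.3 = 77.3 days before that.
- A wear in the 14 days before the third visit starts at 182.6 − 14 = 168.6.
- A wear in the 14 days before a 3-month second visit starts at 91.3 − 14 = 77.3.

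| Reading | Wear (days) | Baseline value | 6-month value | Change computable |
|---|---|---|---|---|
| Visit narrative as written | 91–105 | no | no | no |
| Device description, second visit at 3 months | 77–91 | no | no | no |
| Device description, tied to the 6-month OGTT | 169–183 | no | yes | no |
| Section 4, worn when distributed, visit 2 at 3 months | 0–14 and 91–105 | yes | no | no |
| Section 4, with visit 2 placed 14 days before visit 3 | 0–14 and 169–183 | yes | yes | yes |
| Table 4 taken literally | from baseline, 3 and 6 months | yes | yes | yes |

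The change is computable under two of the six. This is a list of readings and says nothing about how likely each one is.

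**How firm are the two favourable readings?**
- The fifth row combines section 4 with Exposure measures. It conflicts with the narrative's 3-month second visit. It also conflicts with section 4's own calendar, where the visit 2 phase runs from 07/11/2022 to 06/07/2023 and the visit 3 phase opens on 07/07/2023. A 14-day gap could then hold only for participants seen near the end of the visit 2 phase.
- The sixth row rests on the Table 4 marks. The table has 9 sociodemographic + 6 anthropometric (with step counts) + 6 questionnaire (with the dietary record) + 4 glycemic = 25 rows. All 25 carry the same three marks, date of birth included. The marks may be real or may come from text conversion.

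**The case against.** The strongest reply is that the narrative is silent on CGM at baseline and 6 months and does not exclude it. The two glycemic lists quoted from it are lists of results retrieved from clinic records, where a sensor supplied by the study would not appear. The narrative is also plainly incomplete. It leaves out body weight, which the anthropometry text measures at all three visits, and the food frequency questionnaire, which the diet text places at the second visit. That stands. A reader might infer that CGM was never planned at baseline, or that neither value exists. The documents do not support either inference, because section 4 distributes sensors at baseline.

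The second reply is that section 4 and Exposure measures together describe a workable design: one wear at baseline and one ending at the third visit. That also stands as a possible reading, and on it the 14-day sensor life causes no difficulty. It is not established, because the narrative's visit timing and the section 4 calendar both contradict it.

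The third reply is that Table 4 is the formal schedule and marks all three visits, and that it is circular to discount it because the narrative collects less. This is fair as far as it goes. The uniform marks remain a reason for caution that does not depend on the narrative, and they neither prove nor rule out three wears. Figure 3, of which the protocol says "An overview of the study procedure is illustrated in Figure 3", might decide the intended schedule, but it was not available. Even if it showed three wears, the narrative, the device description and section 4 would still need correcting.

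Finally, the stated use of CGM to study meal timing against the food diary needs only a level, so that use does not depend on a change being available.

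**Conclusion.** The concern holds as an inconsistency that leaves one main outcome undetermined. Followed as written, the visit narrative supplies 0 of the 2 values that outcome 4 needs. The device description supplies at most 1. Section 4 supplies 1 or 2, depending on when visit 2 falls. Table 4 read literally supplies both. The stronger claim that the CGM change cannot be computed at all is not supported, since two readings allow it. The opposite claim, that Table 4 settles the matter, is not supported either.

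The conclusion rests on the text alone, without Figure 3 or the Gantt chart, and on wear starting at distribution where no other time is given. The day counts locate the wears and do not measure bias. HbA1c, FPG and 2-hour glucose are not affected by this point, because the narrative obtains them from medical records at both baseline and the third visit.

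**What to change.** 1. Before any CGM outcome analysis, tabulate from the CGM download dates which wears each participant had and when. The device description says that these data are readily accessible.
2. Reconcile the synopsis outcome, the visit narrative, Table 4, the device description, Exposure measures, Study Outcomes, Statistical Analysis, section 4 and Figure 3 to one CGM schedule.
3. If baseline and 6-month wears both exist, keep outcome 4, and make Study Outcomes and Statistical Analysis say that the CGM variable analysed is the change.
4. If they do not, restate outcome 4 as the CGM level from the wear that was done, give its timing, and drop the 6-month change for CGM.
5. In either case, state openly that the schedule or the outcome wording was clarified after the planned end of data collection. Base the choice on wear dates alone, without sight of CGM results.

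The cost is a records check and rewording. If only one wear was done, the claim about CGM change is lost. If both exist, the outcome is kept unchanged.

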1. INTRODUCTION AND JUSTIFICATION OF THE STUDY

Diabetes Mellitus is the chronic non-communication diseases which elevated blood glucose level and human body unable to utilize it effectively, hence cause rise of complications to microvascular and macrovascular damage (IPH, NIH and MOH, 2019). There are about 463 million of patients aged 20 until 79 years old diagnosed diabetes in worldwide (IDF, 2019). It showed an increasing trend adults living with diabetes from 108 million in year 1980 until 422 million in year 2014 (IDF, 2019). International Diabetes Federation, (2019) estimated diabetes will affected in 578 million of adults globally in year 2030 and it reach up to 700 million of worldwide adults in year 2045. 373.90 million western pacific people had impair blood glucose commonly among adults aged 20 years old until 79 years old and it is the highest in global(IDF, 2019). 8% of western pacific adults had impaired glucose tolerance and 55.8% of them are undiagnosed diabetes (IDF, 2019).

Malaysia is one of the countries in Western Pacific region and have Peninsular Malaysia and East Malaysia which separated by South China Sea (Hussein *et al.*, 2015). In the latest Malaysia National Health and Morbidity Survey, the total diabetes incidence among adults ages 18 years old and above in Malaysia is about 3.9 million (18.3%), which indicated that 1 in 5 Malaysian adults have diabetes (IPH, NIH and MOH, 2019). The highest prevalence of diabetes found in state Negeri Sembilan (33.2%), followed by Perlis (32.6%) and Pahang (25.7%) (IPH, NIH and MOH, 2019). The rise of diabetes, hypertension and cholesterol increase the risk to develop cardiovascular disease and it leading to death (IPH, NIH and MOH, 2019). There are 1.7 million Malaysian adults stay with these three major risk factors of cardiovascular disease (IPH, NIH and MOH, 2019). Besides, 1 in 4 adults in Malaysia are physically not active and 95% of adults did not consume recommended both fruits and vegetables (IPH, NIH and MOH, 2019). Sugar are the preferable substitute in self-prepared drinks (coffee, tea, chocolate and malt beverages), and 4.2% adults in

Malaysia drink carbonated drinks and non-carbonated drinks daily. Instant drink products contained sugar also another choice of adults Malaysian daily (IPH, NIH and MOH, 2019). The development of diabetes related module by Ministry of Health and Malaysia Diabetes Educators Society emphasize 7 section diabetes management (MDES, 2020), included assessment, healthy eating, physical activity, medication, self-monitoring , disease complications and behavior. Despite the numerous strategies have been implemented by Malaysian government, however, it has failed to substantially reduce the prevalent of T2DM from prediabetes in Malaysia. Perhaps, there is a missing ingredient in diabetes guidelines today.

Management of excessive caloric intake and promote on exercise are both core lifestyle modification for T2DM which have been recommended in several diabetes management guidelines (MDES, 2020; MOH *et al.*, 2020; WHO, 2020). However, other factors such as dysregulation of circadian rhythms may also contribute to disease development (Onaolapo and Onaolapo, 2018). The growth of chronobiology and evidence on disturbed circadian rhythm contributed to dysfunction of carbohydrate and macronutrients metabolism and it related to hormone melatonin (Onaolapo and Onaolapo, 2018). From a chronobiological point, glucose metabolism in humans follow a circadian rhythm through diurnal variation of glucose tolerance that typically peaks during day-light hours, when food consumption usually happens and reduces when it comes to night-dark hours when fasting usually occurs (Henry, Kaur and Quek, 2020). Unusual meal timings can cause glucose intolerance by affecting the phase relationship between the central circadian pacemaker and peripheral oscillators in cells of the liver and pancreas in rodents (Bandin *et al.* 2015). Similarly in humans, timed meal intake is also driven by the suprachiasmatic nucleus, play a role in synchronization of circadian rhythms in peripheral tissues, thereby affecting glucose metabolism (Henry, Kaur and Quek, 2020). The effects of diet on circadian rhythmicity clearly involves a relationship between factors such as meal timings and nutrients (chrononutrition), that can contribute to circadian perturbation and influence the manifestation of metabolic disorders such as type 2 diabetes; by extension, circadian timing may also be important in prevention of T2DM development from prediabetes. A new concept is born: perhaps it is not what you eat but when you choose to eat it.

In Malaysia, there are no specific guideline for prediabetes individual and they are managed according to the latest Clinical Practice Guideline in Malaysia (MOH *et al.*, 2020). For prevention prediabetes to further develop to diabetes, lifestyle intervention such as weight loss (5-10% of initial body weight), regular physical activity (150 min/week), with dietary strategies including reduced calories and behavior modification are recommended in Clinical Practice Guideline in Malaysia (MOH *et al.*, 2020). A high fibre diet (20-30g/day with 5 to 7 servings/day) consisting of vegetables, fruits, legumes and whole grains is encouraged too (MDES, 2020). All the prediabetic individuals will be referred to dietitian and nurse educators for 6 months routine treatment, prior to T2DM diagnosis, determined by second-round of oral glucose tolerance test (OGTT) in 6-month period (MOH *et al.*, 2020). To the puzzlement of many diabetes researchers and clinicians, some of the prediabetes cases showed tremendous improvement in their blood sugar result, yet some of the prediabetes

individuals developed full-blown of T2DM with their blood sugar result higher than the normal range; despite all of them followed the same routine treatment from healthcare clinics. Perhaps, besides the usual routine treatment from Clinical Practice Guideline (MOH *et al.*, 2020) (weight management, physical activity advices and dietary modification); prediabetic individuals who able to improve their blood sugar result in 6-month period has particular meal-timing, compared to those has uncontrolled blood sugar result in 6-month period.

Although clinical practice guideline applied in the routine treatment does not include meal-timing advices, but the importance of circadian rhythms in regulating mammalian physiological responses has been recognized (Mezitis and Bhatnagar, 2018). Mezitis and Bhatnagar, (2018) from United States of America (US) has emphasized the importance of circadian timing in people with diabetes because insulin sensitivity has been shown to exhibit circadian rhythmicity. Glycemic responses to meals are exaggerated in prediabetes and diabetes patients, more so when the meal is timed to be consumed out of sync with the metabolic pacemaker. Accordingly, Mezitis and Bhatnagar, (2018) have recognized optimal hormonal and hepatic function beginning in the early morning (4:00 a.m.) and fading in the early evening (4:00 p.m.). However, the times proposed by Mezitis and Bhatnagar, (2018) suitable for diabetes patients in US, and might not be able to apply in Malaysia diabetes management. This is because circadian timing system is affected by factors consisting of cosmic events related to the universe and earth, environmental factors (light, night and day duration, seasons) and lifestyles. To the best of our understanding, neither have there been any studies that have exploring the new concept of circadian timing in Malaysia prediabetes individuals, nor in Southeast Asia. The outcome of the present study will be able to recognize the optimal-meal-timing (chrono-nutrition) and activity/ sleeping (chrono-type) among Malaysian prediabetic individuals, in order to prevent prediabetes individuals from developing T2DM. Figure 1 shows the theoretical framework of the present study, adapted from Henry, Kaur and Quek, (2020). The theoretical framework shows that a schematic representation outlining the factors affecting the circadian clock system. Meal timing and dietary components (chrono-nutrition) play an important role in regulating circadian clocks, to enhance metabolic health and reduce the risk of type 2 diabetes. These recommendations could be considered as strategies to improve glycemic control, rather than focusing on the nutritional value of a meal alone, to optimize dietary patterns of diabetics. It is necessary to further elucidate this fascinating area of research to understand the circadian system and its implications on nutrition that may ultimately reduce the burden of type 2 diabetes.

[figure not shown]

Figure 1 Theoretical framework showed factors affecting circadian rhythm.

The investigator propose that the individual is nested within their environment which includes the influences of social demands e.g. social timing resulting from demands such as school or work schedules, social activities, family obligations and routines, parenting practices, community involvement, time zone, etc., the modern lighting and climate controlled environment, as well as the effect of the earth's natural environment. Within the individual, there is an interdependence of the circadian clocks, behavior, and health. The major contribution of this model is that the circannual clock interacts with the circadian clocks to promote optimal glucose tolerance of individual's circannual influences may have health consequences. The investigator propose interactions within the individual and across levels of this model. For example, social demands influence an individual's behavior which affects alignment of the clocks either by direct entrainment of the peripheral clocks (i.e., meal timing and consistency) or by affecting exposure to the light-dark cycle via sleep timing and consistency, physical activity, and exposure to artificial light at night. It is also proposed that circadian disruption caused by the environmental factors may contribute to disruption of circannual rhythms of growth, resulting in accelerated blood sugar and contributing to the development of type 2 diabetes mellitus.

[figure not shown]

Figure 2 Conceptual framework

Identifying novel, potentially modifiable, life-style factors associated with increased blood sugar level, can lead to innovative strategies for improving health status and preventing T2DM in prediabetes individuals. The proposed study presents a novel approach as a paradigm shift in Malaysia diabetes management. The investigator anticipate that this study will not only reveal the optimal-meal timing (chrono-nutrition) for prediabetic individuals, it will also disclose the associations of chrono-nutrition with glycemic measures and anthropometric measurements in prediabetic individuals. The findings may act as guidance to government bodies to develop policies at national level. For non-governmental agencies, the outcome may be applied to plan public campaigns to improve blood sugar outcome in prediabetic and diabetic individuals. Besides, optimal-meal timing and factors associated with chrono-nutrition would be identified and management of these factors can be delivered to diabetic individuals. For example, improvement of the dietary pattern and timing coupled with physical activity to ensure good blood sugar control. Understanding the optimal-meal-timing for blood sugar control could tailor education and intervention in diabetes management. This research has potential to be converted into a larger cohort study and intervention whereby prediabetic individuals could be follow-up for longer duration to study health outcomes and blood sugar control to manage the diabetes

